### 5.6 Masking/Blinding of Study

This is a double-blinded study; subjects and clinical investigators (physicians, nurse practitioners and study delegates) will be blinded to the treatment. Study treatments (either TP or control PCCA PP base) will be packaged at the Mayo Clinic Compounding Pharmacy as described above. Compounding pharmacists will be aware of the study drug and will provide an unidentified label (please see example in Section 5.5) with lot number only for each treatment application. At the completion of the study, investigators will be unmasked following data interpretation and statistical analysis.

### 5.7 Receiving, Storage, Dispensing and Return

Per Mayo Clinic Research Pharmacy policy, investigational product(s) are received by study personnel acting on behalf of the investigator. Research pharmacy staff verifies information on the packing slip matches the contents of the shipment. The following are verified by receiving personnel upon receipt of shipment: product identification, sponsor product label, quantity of items received, package size(s), lot numbers, expiration dates if available, product condition, and maintenance of storage conditions in transit. Any discrepancies in shipment are communicated immediately to study sponsor. Investigational products that do not contain an expiration date are deemed in date and acceptable to use until notice of expiration is received from sponsor or supplier. Research staff contacts sponsors and/or suppliers quarterly to determine if retest date or expiration is available. After shipment has been checked and verified, IP is immediately placed in appropriate storage conditions as indicated in study documentation. For product delivered with a temperature recording device which may be electronically interrogated, data will be downloaded and saved in PDF format in the Investigational Drug Services (IDS) electronic management application if the device supports such function.

Invoices are dated, signed, scanned, and uploaded electronically into the IDS electronic management application at time of receipt. Signed/dated hard copies of invoices are double checked per page against scanned uploaded images to ensure scanned image represents a true copy of the original document. Once accuracy of the scanned image has been verified, hard copies of invoices/shipping documents are discarded.

---

**Product NDC****No No.**

---

11310	63323-	PENTAM® 300 (pentamidine isethiionate for injection) 300 mg, 113-10 lyophilized product in single-dose vials, packages of 10.
-------	--------	----------------------------------------------------------------------------------------------------------------------------------

---

Store dry product at 20° to 25°C (68° to 77°F) [see USP Controlled Room Temperature]. Protect from light. Preservative Free. Discard unused portion.

Mayo Clinic compounding pharmacy will produce the topical gel pentamidine (Pentam-300) in PCCA PP in USP (U.S. Pharmacopeial Convention)-grade facility. This gel is then sent to the research pharmacy in single dose containers and stored at controlled room temperature (20-25°C) and stable until the end of the study period (4 weeks).

Study coordinators will pick up study drug containers from the research pharmacy for dispensation to the patient. Any unused doses will be returned to the research pharmacy to be discarded properly.

### **5.7.1 Receipt of Drug Supplies**

All drug formulation and compounding will be performed in the Mayo Clinic Compounding Laboratory. Pentam-300 and PCCA PP will be purchased from their respective manufacturers and shipped to the Research Pharmacy. Purchase will occur via Mayo Clinic Rochester Methodist Campus (RMC) pharmacy purchasing specialists from APP Pharmaceuticals. Further production details in Section 5.5. This is a single-site study conducted in Mayo Clinic Rochester, MN.

### **5.7.2 Storage**

The compounded drug will be stored at controlled room temperature (20-25°C) in light resistant containers placed in amber Ziploc bags. These will be kept secure in the Research Pharmacy until receipt of compounding request from the clinical trial coordinator. Special access is required to access this location to prevent unintended or unauthorized use of the drug. No special handling is required. Since the drug is formulated from a lyophilized, stable product and compounded with a non-aqueous base, the topical formulation will be stable for up to 180 days.

Per Mayo Clinic Research Pharmacy policy, the Investigational Pharmacy is a secure, badge access area accessible to authorized pharmacy personnel only. Investigational products are stored as per study documentation. Temperature monitoring is recorded via a continuous electronic monitoring system. All storage areas and devices that contain investigational products are monitored by this system. Temperature sensor devices are calibrated per local policy and calibration certificates are available upon request. Sponsor specific temperature monitoring devices are not utilized. Temperature data from the continuous electronic temperature monitoring system is stored

electronically in a dedicated server and is readily retrievable upon request. Local procedures are followed in the event of an out of range condition reported by the continuous electronic monitoring system.

### **5.7.3 Dispensing of Study Drug**

Per Mayo Clinic Research Pharmacy policy, pharmacists and/or pharmacy technicians under the supervision of a pharmacist will prepare and dispense investigational products per study protocol. Lot numbers and expiration dates of commercial supplies utilized in the preparation of investigational products such as syringes, needles, IV bags, tubing, diluents, and standard of care products are not tracked.

Single dose containers will help to ensure accurate and consistent dosing across all patients participating in the trial. Approximately 1.8 mL (0.06 oz) of TP and placebo PCCA PP will be topically applied to the designated scar region. The randomized treatment group (TP versus PCCA PP) will be assigned to subjects in a double-blinded manner by the research pharmacist; details in Section 5.5. Patients will be educated on topical drug application during the pre-operative clinic visit. The patient will be instructed to apply enough study drug to thoroughly cover the area to be treated. It is not necessary to use the entire dose for each treatment application, but a minimum of at least half should be used. The patient will be asked to administer a sample product in the presence of a study coordinator to verify their application technique and amount. Once the patient demonstrates understanding and skill, the patient may personally administer the remaining treatments during the trial.

Single dose containers will be distributed to patients at visit 2 and visit 3. Each treatment set will contain 8 active and 8 placebo containers to be applied every 48 hours. Any unused containers will be returned by the patient at their next follow-up visit (return bag for used containers will be provided). Randomized treatment label will contain instructions for site-specific application. Patients are held accountable for keeping track of dispensed drug at all times. If a dose of the drug is lost due to unforeseen circumstances, a single replacement may be available.

Regular study drug reconciliation will be performed to document drug assigned, drug dispensed, drug returns, and drug remaining. This reconciliation will be logged on the drug reconciliation form, and signed and dated by the study team.

### **5.7.4 Return or Destruction of Study Drug**

Per Mayo Clinic Research Pharmacy policy, investigational product and associated wastes generated on site as a consequence of participation in a sponsor's study are disposed of via placement in a designated, appropriate waste container per local policy and regulation. Empty containers, vials, or empty injectable syringes of investigational products generated from preparation and subsequent administration of an investigational product to a patient are not retained for monitor inspection following dose preparation; instead these items are disposed of by placement in an appropriate waste container based on the hazard risk of the investigational product (e.g. hazardous, chemotherapeutic, biohazardous). Disposition is documented in the IDS electronic management application. Unless pharmacy is the only unblinded party in a study, IDS pharmacy staff will not document investigational product destruction or drug returns within sponsor electronic systems. In addition, all investigational products (i.e. tablets, capsules, injections, and/or

containers) that are returned by subjects, as well as any returned empty boxes and cartons are disposed of in the manner described above immediately after appropriate documentation of such return has occurred in the IDS electronic management application.

At the completion of the study, there will be a final reconciliation of amounts of cream manufactured, dispensed, returned (if applicable), destroyed and any drug remaining. This reconciliation will be documented, signed and dated. Any discrepancies noted will be documented and investigated, prior to return or destruction of unused study drug. Drug destroyed on site will be documented in the study files.

## 6 Study Procedures

### 6.1 Visit 0 (Preoperative screening)

Patients will provide written consent if they are interested in participating in this trial and meet appropriate inclusion and exclusion criteria.

[figure not shown]
### 6.2 Visit 1 (Preoperative period)

Patients will receive a comprehensive pre-operative evaluation. This evaluation will gather information relating to medical history as well as include a standard clinical exam and necessary laboratory studies. Once consent is provided and patient meets inclusion criteria as a qualified participant for the study, photographs will be taken of the lesion area with a digital camera and/or photography service. Pre-operative ultrasound and/or 3D imaging will also be performed to determine initial scar height and morphology. The scar will be assessed using the Vancouver Scar Scale (VSS) [28] and the Patient and Observer Scar Assessment Scale (POSAS) [29]. These scales will determine the initial level of hypertrophy and scar attributes before treatment initiation. Safety evaluation will include assessment of systemic and local safety and thus baseline clinical exam with neuropsychiatric evaluation, laboratory studies (including hepatic and renal function, complete blood count with differential, blood glucose level and calcium) and baseline cardiac monitoring with electrocardiogram (ECG) will be performed.

This visit will include two 5-mm skin punch biopsy (one from distal site and one from proximal scar site) performed under local anesthesia in a dedicated procedure room. Alternatively, the first punch biopsy may occur prior to the surgical procedure while under anesthesia. This sample will be processed by the study staff for histological/molecular evaluation to analyze scar characteristics.

Patients will also be educated on proper treatment application. Treatment regimen and duration will be summarized. For example, following their surgical scar excision procedure, they will be provided single dose containers with topical study agents. There will be two different formulations given to patients; one is the placebo control (PCCA PP) and the other is the active treatment (TP). Patients and providers blinded to treatment regions but their treatment label will have appropriate instructions for application either at the distal or proximal region.

Based on the distal or proximal region assigned to each formulation by the pharmacist and appropriately labeled single dose containers, patients will apply the unit dose. Compound A (either TP or PCCA PP) will be applied to proximal site and Compound B (either TP or PCCA PP) will be applied to the distal site; 1-2 cm border zone in the middle of the scar will remain untreated.

The study coordinator will provide a demonstration of application using a sample container containing petroleum gel or similar non-therapeutic agent. Prior to treatment application, site preparation and wound care techniques will be reviewed (patient education hand-out provided). Patients will be advised to carefully clean the skin around the wound using either normal saline solution or mild soapy water. Using medical gloves, topical gel will be applied to either the proximal or distal wound. Gloves will be changed between each treatment application. Patients will then practice topical gel application and wound dressing to verify their understanding. Regarding total surface area to be treated, the following guidelines are recommended:

- Scar length 3 cm to 8 cm: Treat 2 cm proximal (site A) and 2 cm distal (site B)
- Scar length 8 cm to 10 cm: Treat 3 cm proximal (site A) and 3 cm distal (site B)
- Scar length 10 cm to 15 cm: Treat 4 cm proximal (site A) and 4 cm distal (site B)
- Scar length >15cm: Treat 5 cm proximal (site A) and 5 cm distal (site B)

After each treatment application, the treated area will be covered with a non-adherent dressing (which will be provided to the patient). There will be a 1-2 cm untreated gap between the two scar treatment sites (proximal and distal to prevent cross contaminations).

At this visit, a detailed schedule will be provided including date of surgery and follow-up visits/phone calls. All procedures, surveys, imaging and testing will be explained.

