## 3 Study Design

### 3.1 General Description

This study is a double-blind pilot study of scar excision procedure followed by treatment with either TP in PCCA PP versus PCCA PP silicone base only. Current management for patients with hypertrophic scar includes silicone-based treatment. At our institution we treat patients with scar excision surgery without topical scar cream following the procedure. However, a significant proportion of patients continue to fail this treatment modality leading to scar recurrence. Indeed, individual patient response to therapy varies based on patient characteristics including ethnicity. As such, we plan to treat the same patient with both TP in PCCA PP and PCCA PP alone at different ends of their scar. In this way, we can better determine efficacy of these topical agents in biologically controlled setting with reduced response variability. We plan to enroll patients with minimum hypertrophic scar length  $\geq 3$  cm.

Those patients who successfully qualify based on inclusion and exclusion criteria will be invited to participate in the trial. Following informed consent, eligible subjects will undergo pre-operative tests to include blood work and EKG. Preoperative photographs of the scar site will be taken. Scar quality questionnaires (VSS and POSAS) will be completed and a scar ultrasound performed.. A 5-mm skin punch biopsy will be obtained from the lateral edge of the scar at both the proximal and distal ends of the scars, under local anesthesia. Alternatively, the first punch biopsy may occur prior to the surgical procedure while the patient is under anesthesia. Part of the sample will be stored in formalin and prepared for histological staining. The other portion will be frozen and prepared for molecular analysis. All participants will receive both treatments to be applied either at the proximal end or the distal end of the scar. Treatment application will be randomized. For example, topical agent A will be applied to the proximal end of the scar and will contain either TP

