## 4 Subject Selection Enrollment and Withdrawal

### 4.1 Inclusion Criteria

- Males and females 18 years of age or older.
- Diagnosis of hypertrophic scar by a Mayo Clinic plastic surgeon or dermatologist
- Target disease or condition: Hypertrophic scar
- Subject with a hypertrophic scar that meet all of the following criteria:
  - Linear scar  $\geq 3$  cm to  $\leq 40$  cm in length
  - Present for minimum 6 months
  - Located anywhere in the body except on the face or front of neck
  - Resulting from surgical or traumatic injury, or other scar considered appropriate for surgical excision
- Ability to safely undergo scar excision surgery
- Capacity to provide informed consent
- Ability to comply with protocol
- Subject is judged, by the clinical investigator, to be healthy as evidenced by lack of clinically significant abnormal findings on medical history, physical examination, electrocardiogram, vital signs, and clinical laboratory tests.

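### In scars of 3 to under 5 cm, the recommended 2 cm treated zones in section 6.2 do not leave room for the 1-2 cm untreated gap, and no shorter zone is given (minor).

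*Combined protocol and SAP*

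**What the plan says.** Section 3.1 states "We plan to enroll patients with minimum hypertrophic scar length" of 3 cm or more. Section 4.1 introduces its scar requirements with "Subject with a hypertrophic scar that meet all of the following criteria" and sets the length at 3 to 40 cm. Each patient uses pentamidine gel at one end and the silicone base at the other.

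Section 6.2 introduces the treated lengths with "Regarding total surface area to be treated, the following guidelines are recommended". The lowest band reads "Scar length 3 cm to 8 cm: Treat 2 cm proximal (site A) and 2 cm distal (site B"). The higher bands give 3 cm per end for scars of 8 to 10 cm, 4 cm for 10 to 15 cm, and 5 cm above 15 cm.

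The untreated middle is worded more firmly. Section 6.2 says "1-2 cm border zone in the middle of the scar will remain untreated" before the bands and "There will be a 1-2 cm untreated gap between the two scar treatment sites (proximal and distal to prevent cross contaminations") after them. Section 3.1 gives the same border zone.

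The gel goes on after excision: section 6.2 says "topical gel will be applied to either the proximal or distal wound". The bands, however, are set by scar length, and no section gives the length of the wound. Section 5.7.3 lets the patient use less than a full container (enough to cover the area, and at least half) but does not shorten the treated zone.

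**The concern.** The lowest band names 3 cm as its lower limit, yet two zones of 2 cm already exceed a 3 cm scar before any gap is left. Staff who meet a short scar have two instructions that cannot both be carried out, and no substitute length.

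The gap protects the within-patient comparison. If both zones are drawn at 2 cm in a scar under 4 cm, a strip in the middle receives both gels. A local reaction there, such as erythema or ulceration, cannot be assigned to pentamidine or to base. The Study Summary plans a descriptive primary analysis that contrasts adverse events between lesions, so attribution by site matters. With ten subjects (section 3.2), each patient is a tenth of the data. Patients apply the gel themselves at home, and section 1.6.4 treats a standard application technique as critical, so the zone length is better fixed in writing than left to judgement.

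**Working it through.** **Inputs.** Lowest eligible scar length: 3 cm (sections 3.1 and 4.1). Zone length for scars of 3 to 8 cm: 2 cm per end (6.2). Untreated gap: 1-2 cm (3.1 and 6.2), read here as at least 1 cm. The plan states no figure of its own to reproduce.

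**Assumption.** Let L be scar length and W the length of the wound to which gel is applied, with W = L + e. The documents do not give e. The main case is e = 0, and larger values are shown as a range.

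**Length needed for both instructions.** 2 + 2 + 1 = 5 cm, against a minimum of 3 cm. If the gap had to be 2 cm, the length needed would be 6 cm.

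**Main case (e = 0).** Gap = L - 4 when this is positive. Overlap = 4 - L when this is positive. Share of each zone that receives both gels = overlap / 2.

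| L (cm) | Overlap (cm) | Share of each zone | Gap (cm) |
|---|---|---|---|
| 3 | 1 | 50% | none |
| 3.5 | 0.5 | 25% | none |
| 4 | 0 | 0% | 0 |
| 4.5 | 0 | 0% | 0.5 |
| 5 | 0 | 0% | 1 |

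**Longer wound.** Overlap occurs for scars under 4 - e cm, and the gap is below 1 cm for scars under 5 - e cm.

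| e (cm) | Overlap for scars under | Gap short for scars under |
|---|---|---|
| 0 | 4 cm | 5 cm |
| 0.5 | 3.5 cm | 4.5 cm |
| 1 | no eligible scar (4 - 1 = 3) | 4 cm |
| 2 | no eligible scar | no eligible scar (5 - 2 = 3) |

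**Other bands.** The smallest gap is 8 - 6 = 2 cm in the second band, 10 - 8 = 2 cm in the third, and more than 15 - 10 = 5 cm in the top band. Only the lowest band can fall short of 1 cm.

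**Check of the remedy.** The longest equal zone that keeps a 1 cm gap is (L - 1)/2, which is 1 cm at L = 3, 1.5 cm at L = 4 and 2 cm at L = 5. Fixed steps at these values give:

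- 3 to under 4 cm, 1 cm per end: gap L - 2, from 1 to under 2 cm.
- 4 to under 5 cm, 1.5 cm per end: gap L - 3, from 1 to under 2 cm.
- 5 to 8 cm, 2 cm per end: gap L - 4, at least 1 cm.

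**The case against.** The strongest reply is that the wording already ranks the two instructions. The lengths are recommendations, while the gap is stated three times as something that will be left, once with its purpose. A sensible coordinator would keep the gap and shorten the zones. Overlap would need conduct at odds with those statements, and section 6.2 adds glove changes, a demonstration and supervised practice. This largely stands. It reduces the point to a missing substitute length, but it does not supply that length.

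Second, gel is applied to the wound, which may be longer than the scar. This also stands, and the second table shows how quickly the conflict shrinks. However, the bands themselves are written in scar length.

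Third, the 1-2 cm figure may be approximate, because the bands leave more than 2 cm in many longer scars (3 cm in a 7 cm scar, 7 cm in a 15 cm scar). That is why the gap is read here only as a minimum. A wider gap does not threaten the separation of the two sites.

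A reader might go further and infer the following, none of which the documents support:

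- *That the efficacy measures are contaminated.* The plan does not say that ultrasound, VSS or POSAS are taken over the whole treated zone. They are affected only if they are.
- *That histology is affected.* It may escape. The shared strip lies in the middle, and a 5-mm punch fits in the outer 1 cm of each zone even at 3 cm.
- *That serious adverse events in Aim 1 cannot be attributed.* Most serious events listed in section 8.1, such as death or hospitalization, belong to the patient and not to a site. A local event such as tissue necrosis could be affected.
- *That patients will receive both gels on the same tissue.* This requires a scar under 4 cm, literal use of the guideline, and a wound less than 4 cm long.

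**Conclusion.** The point holds as a narrow inconsistency in section 6.2. With wound length equal to scar length and a gap of at least 1 cm, eligible scars of 3 to under 5 cm cannot meet both instructions. The harm identified is limited to scars under 4 cm in which the recommended lengths are followed literally: up to half of each zone, at 3 cm, would receive both gels, and a local reaction there could not be assigned to one product. From 4 to under 5 cm the separation is merely shorter than planned. The arithmetic is certain; the reach is not. Scar and wound lengths of enrolled patients are not given, and the number affected could be zero. The patient hand-out is not among the documents, so it may already cover short scars. Severity: minor.

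**What to change.** State in section 6.2 and in the patient hand-out that an untreated gap of at least 1 cm takes precedence over the treated lengths. Split the lowest band in three: 1 cm per end for scars of 3 to under 4 cm, 1.5 cm for 4 to under 5 cm, and 2 cm for 5 to 8 cm. Scar length is known at Visit 1, when patients are taught. Using it is cautious if the whole scar is excised, because a longer wound only widens the gap.

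Leave the amount of gel to the existing rule in section 5.7.3. No separate half-packet instruction or label change is needed. Telling patients to use about half would put them on that section's minimum, where a small shortfall breaches it. Raising the minimum scar length to 5 cm would also resolve the conflict, but it narrows recruitment and is not necessary.

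The cost is a few lines in the protocol and hand-out, submitted to the IRB as a minor amendment (section 11), and a smaller treated area in scars under 5 cm. A 5-mm biopsy still fits in a 1 cm zone. Sample size and visits do not change, and neither does eligibility.
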